Study design	All subjects underwent height, weight, waist and hip, hip circumference, blood pressure, hairy score, blood biochemistry (blood routine, liver and kidney function, electrolyte, thyroid function, fasting blood glucose, glycated hemoglobin, insulin release test, inflammatory markers, sex hormones, eight items), gynecologic color Doppler ultrasound and glucose clamp examination before admission. After informed consent was obtained, 1ml of the remaining plasma was collected and frozen in the refrigerator at -80°C. Patients with $BMI \geq 24 \text{ kg/m}^2$ or waist circumference $\geq 85 \text{ cm}$ were randomly assigned to GLP-1RA + metformin or Diane-35 + metformin. After 1 month, all subjects were examined: height, weight, BMI, waist circumference, hip circumference, waist-to-hip ratio, menstrual history, hirsutism score, diet, exercise frequency and intensity, blood pressure and blood biochemistry. After 3 months, the general condition of all subjects and general biochemical tests such as blood lipid, liver and kidney function, fasting blood glucose, glycated hemoglobin, insulin release test, inflammation markers and gynecological color ultrasound were tested again, and 1ml of plasma was collected and frozen in the refrigerator at -80°C.
Trial objective	
 Provide new treatments for overweight or obese patients with PCOS. Improve PCOS and establish regular menstrual cycles by reducing weight and correcting metabolic disorders.
Name and specifications of the required drugs or equipment Grid, manufacturer, and quantity	Metformin enteric coated tablets: Hebei Tiancheng Pharmaceutical Co., Ltd., trade name: Junshida, dosage: 0.5g orally 3/day; Liraglutide injection: Novo Nordisk, Denmark, trade name: Novo Nordisk, dosage: 0.6mg subcutaneous injection once a day, increased to 1.2mg after 1 week, maximum dose is 1.8 mg/d; Acetylenylestradiol cycloproterenone tablets: Bayer AG, Germany, trade name: Diane-35, dosage: 1 tablet taken orally starting from the first day of the menstrual cycle, Take 1 tablet daily for 21 consecutive days, discontinue for 7 days.

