Statistical analysis

Title of the study	The Effect of GLP-1 Agonists Versus OCs on Reproductive Disorders and Cardiovascular Risks in Overweight PCOS
NTC Number	NCT03151005
Statistical method	Statistical analyses were performed using SPSS 23.0 and GraphPad Prism 8. For normally distributed continuous variables of clinical parameters, variables are described as the mean \pm standard deviation (SD), a paired t-test was used to compare pretreatment and posttreatment values of continuous variables in each of the treatment groups, and between-group differences were compared by an independent sample t-test. For nonnormally distributed continuous variables, the nonparametric Wilcoxon signed-rank test for related samples was used to compare pretreatment and posttreatment values in each of the treatment groups. The chi-square test was used for counting data. To compare the changes in clinical parameters between different treatment groups, the nonparametric Mann-Whitney test was used. Proteomic data analysis was described by proteomic data acquisition and analysis. Protein levels are described as the mean \pm standard error of the mean (SEM), and a paired t-test was used to compare plasma protein levels measured by ELISA. Pvalues <0.05 were considered statistically significant.
Document Date	July 28, 2017

Table 1-Baseline and posttreatment characteristics of clinical parameters after 12-week of treatment.

Characteristics	CPA/EE+Met(n=30)			GLP-1 RA+Met(n=30)		
	Baseline	Posttreatment	Pvalue	Baseline	Posttreatment	Pvalue
Biometric features						
Weight(kg)						
BMI (kg/m ²)						
Waist(cm)						
WHR						
SBP(mm/Hg)						
DBP(mm/Hg)						
Reproductive function						
Dominant follicle,n(%)						
Regular menstruation, n(%)						
Amenorrhoea, n(%)*						
Oligomenorrhoea,n(%)†						
Polycystic ovaries according to Rotterdam criteria, n(%)						
T(nmol/L)						
LH(mIU/ml)						
FSH(mIU/ml)						
LH/FSH						
DHEA-S(ug/dL)						
SHBG (nmol/L)						
FAI						
E2(pg/ml)						
P(ng/ml)						
PRL(ng/ml)						
Biochemical profile of glucose metabolism						
HbA1c(%)						
HbA1c(mmol/mol)						
FBG(mmol/L)						
AUCI						
FINS(uU/ml)						
HOMA-IR						
Biochemical profile of lipid metabolism						
TG(mmol/L)						
TC(mmol/L)						

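### The oligomenorrhoea row of SAP Table 1 gets its own P value, but as the middle menstrual state its count can stay flat or rise when women improve, so that P value shows neither benefit nor harm

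*SAP*

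**What the plan says.** The protocol's second trial objective is "Improve PCOS and establish regular menstrual cycles by reducing weight and correcting metabolic disorders". SAP Table 1, titled "Baseline and posttreatment characteristics of clinical parameters after 12-week of treatment", carries the menstrual results under reproductive function. It has three separate count-and-percentage rows: "Regular menstruation, n"(%), "Amenorrhoea, n"(%) and "Oligomenorrhoea,n"(%). For each arm of 30 the columns are baseline, posttreatment and P value.

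For counts, the SAP's statistical method section says only: "The chi-square test was used for counting data". The threshold is "Pvalues <0.05 were considered statistically significant". The SAP does not order the three states, give a joint test, or say which row addresses the objective. Table 2, which compares changes between arms, has biometric, hormone and lipid rows but no menstrual row.

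**The concern.** Read in the natural way, the three rows are the worst, middle and best levels of one variable. A P value on the best or worst level has a direction: more regular cycles is good, and more amenorrhoea is bad. A P value on the middle level has none, because improvement moves women both into it and out of it. A paired test does not cure this, since the difficulty lies in what is counted.

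At stake is how the menstrual results are read. A flat oligomenorrhoea row could be taken as no effect on cycles, and a significant rise as harm, in an arm where women only got better. Table 2 offers no between-arm menstrual result to set beside it.

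**Working it through.** **Inputs from the documents.** There are 30 women per arm (30 + 30 = 60, matching the protocol's 60 cases), a chi-square test for counts and a 0.05 threshold. Entry requires two of three Rotterdam features, of which oligomenorrhoea is one, so mixed baseline states are possible. No baseline mix or transition rate is given. All counts and rates below are therefore assumptions, and the three states are taken as mutually exclusive.

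**Step 1: the identity.** Write A, O and R for amenorrhoea, oligomenorrhoea and regular. Then

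change in O = (A→O) + (R→O) − (O→R) − (O→A).

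If nobody worsens, this is (A→O) − (O→R), which can be negative, zero or positive. Under the same condition the change in R is (O→R) + (A→R), which cannot be negative, and A cannot rise. Only the middle row loses its direction.

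**Step 2: a flat row.** Baseline A/O/R is 10/15/5; 10 women move A→O and 10 move O→R, giving 0/15/15.
- O row: 15 to 15, discordant pairs 10 v 10, exact McNemar P=1.0.
- R row: 5 to 15, 10 v 0, P = 2 × 0.5^10 = 0.002.
- A row: 10 to 0, 10 v 0, P=0.002.
- Ordered change: 20 improved, 0 worsened, sign test P = 2 × 0.5^20 = 0.0000019.

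**Step 3: a reversed row.** Baseline is 18/12/0; 15 women move A→O and 3 move O→R, giving 3/24/3.
- O row: 12 to 24. Chi-square = 60 × (12×6 − 18×24)² / (30 × 30 × 36 × 24) = 10.0, P=0.0016 (0.0037 with continuity correction). Exact McNemar, 15 v 3, gives P=0.0075.
- R row: 0 to 3, 3 v 0, P=0.25. It is not significant, but it moves the right way.
- Ordered change: 18 improved, 0 worsened, sign test P = 2 × 0.5^18 = 0.0000076.

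**Step 4: how often the O row fails to fall.** First assume no worsening, no regular women at baseline, A→O 60% and O→R 35%. With share s, the number in A is Binomial(30, s), moves in are Binomial(A, 0.60), and moves out are Binomial(30 − A, 0.35). Summing the probability that moves in ≥ moves out:

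| Baseline amenorrhoea | 10% | 20% | 30% | 40% | 50% | 60% |
|---|---|---|---|---|---|---|
| O row flat or rising | 1% | 10% | 34% | 65% | 87% | 97% |

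Second, assume 20% regular at baseline and some worsening: A→O 50%, A→R 10%, O→A 5%, R→O 10%, and O→R as shown. Simulated arms of 30:

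| Baseline A/O/R | O→R | Expected change in O | O row flat or rising |
|---|---|---|---|
| 10/70/20% | 40% | 1.5 + 0.6 − 8.4 − 1.05 = −7.35 | 1.4% |
| 20/60/20% | 40% | 3.0 + 0.6 − 7.2 − 0.9 = −4.5 | 12% |
| 30/50/20% | 40% | 4.5 + 0.6 − 6.0 − 0.75 = −1.65 | 36% |
| 40/40/20% | 35% | 6.0 + 0.6 − 4.2 − 0.6 = +1.8 | 75% |

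The last line uses a slightly lower O→R rate; at 40% the figure is 69%.

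**Step 5: would one ordered test have more power?** Under the second set of rates, comparing exact McNemar on the R row with a sign test on the ordered change (simulation error 1 to 2 points):

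| Baseline A/O/R | O→R | R row | Sign test |
|---|---|---|---|
| 10/70/20% | 40% | 74% | 65% |
| 20/60/20% | 40% | 66% | 75% |
| 30/50/20% | 40% | 52% | 81% |
| 40/40/20% | 35% | 31% | 84% |

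The ordered test wins when amenorrhoea is common and loses when it is rare.

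**The case against.** The strongest reply is that the objective concerns regular cycles and Table 1 has a row for exactly that. That row cannot reverse through improvement, and in the flat case above it is significant (P=0.002). A reader might infer that the plan gives a null or reversed answer on the cycle objective. The documents do not support that: nothing makes the oligomenorrhoea row the answer, and all three percentages are printed together. This part of the reply stands.

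A reader might also infer that three weak tests are replacing one strong one. Step 5 does not support that in general. The sign test also counts a move from amenorrhoea to oligomenorrhoea as success, which is not yet a regular cycle, so part of its advantage comes from a looser definition. This stands too.

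The mechanism may hardly operate in the CPA/EE arm, where treatment runs in cycles of 21 days on and 7 off. If 90% of those women were recorded as regular after treatment (an assumption), the oligomenorrhoea row was flat or rising in 0% of simulated arms at the 30/50/20% and 40/40/20% mixes.

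Finally, the layout is an empty shell. Mutual exclusivity and one P value per row are inferred from it, and the notes behind the * and † marks are not in the supplied text, which is not counted as a fault. A single three-by-two chi-square is not ruled out, but the SAP does not state it, and it would ignore both order and pairing.

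None of these replies gives the oligomenorrhoea P value a direction.

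**Conclusion.** The point holds for one row. If the states are exclusive and each row is tested, as the shell suggests, the oligomenorrhoea P value is uninterpretable as benefit or harm. That follows from the identity in step 1 and needs no assumed rates. How often it would mislead does depend on assumed rates: about 1% of arms at a 10% amenorrhoea share, roughly a third at 30%, and 65% to 75% at 40%. The documents give nothing to say which share applies.

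The cycle objective is still answered by the regular-menstruation row, and no general power gain from an ordinal test is shown. This is a modest fault that is cheap to repair, made more useful to repair by the lack of any menstrual row in Table 2.

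**What to change.** 1. State in the SAP that regular menstruation is the row that addresses the cycle objective, and test it within each arm with a paired test (exact McNemar), since the same women are counted twice.
2. Print oligomenorrhoea and amenorrhoea as description without P values, and add counts of women improved, unchanged and worsened.
3. Define one ordered status per woman (amenorrhoea < oligomenorrhoea < regular), and add one between-arm row to Table 2: Mann-Whitney on change in category.

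The cost is SAP wording and two table shells, with no new data or visits. The SAP already names Mann-Whitney for changes between arms, but McNemar is not named and the text must be extended to ordinal and paired categorical data. The price is fewer familiar P values.

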Inclusion and exclusion criteria	
Inclusion criteria : a) clinical diagnosis of PCOS according to the Rotterdam criteria based on the presence of two of three criteria (3) , oligomenorrhea, clinical or biochemical hyperandrogenism, and polycystic ovaries on ultrasound after exclusion of other endocrine causes of hyperandrogenism; b) participants had no concurrent illness and were not on any prescription or over-the-counter medication that was likely to affect insulin sensitivity or lipids for the preceding 12 weeks; c) participants were advised not to change physical activity or dietary habits during the study period; d) given that all subjects were of Asian ethnicity, overweight was defined as $BMI \geq 24 \text{ kg/m}^2$. e.) all subjects had normal thyroid-stimulating hormone and prolactin levels.
 
exclusion criteria : a) age below 18 years or over 50 years; b) uncontrolled hypertension (blood pressure $\geq 160/100 \text{ mmHg}$); c) signs of liver or renal failure or active liver disease (alanine transaminase (ALT) $> 2.5 \times$ the upper limit of normal values); d) patients who were postmenopausal or pregnant; e) alcohol intake greater than 20 g/day; f) patients who could not complete the intervention or had other conditions that made them ineligible for participation. For example, patients taking glucocorticoid steroids or under treatment for a malignant tumor were excluded.

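### Ovarian morphology is analysed only as yes/no rows, with no between-arm ovarian row, which gives up a substantial part of the power to detect ovarian change with 30 women per arm

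*SAP*

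**What the plan says.** The protocol's Study design lists "gynecologic color Doppler ultrasound and glucose clamp examination before admission", and for the 3-month visit says that "inflammation markers and gynecological color ultrasound were tested again". It does not say which ultrasound measurements are written down.

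In SAP Table 1, under Reproductive function, two rows concern the ovary: "Polycystic ovaries according to Rotterdam criteria, n" and "Dominant follicle,n", each with a percentage. Neither SAP table has a row for follicle number or ovarian size. Table 1 gives a P value for baseline against posttreatment within each arm (n=30 each). Table 2 compares changes between arms for biometric features, sex hormones and lipids, and contains no ovarian row.

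On tests, the SAP's Statistical method section says "The chi-square test was used for counting data" and names no paired test for binary data. For continuous rows, "a paired t-test was used to compare pretreatment and posttreatment values of continuous variables in each of the treatment groups", with rank-based alternatives. The threshold is "Pvalues <0.05 were considered statistically significant".

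Under the inclusion criteria, PCOS is diagnosed "based on the presence of two of three criteria", and polycystic ovaries on ultrasound is one of the three. A woman can therefore enter without it.

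**The concern.** If the yes/no reading reflects a threshold on an underlying ovarian measure, a woman registers a change only when she crosses that threshold. A shift that leaves her on the same side counts as nothing. With 30 women per arm, a non-significant yes/no row could mean either that the ovaries did not change or that the measure was too coarse to show it, and the plan offers no second ovarian result to tell these apart.

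Two features of the analysis add to this. A chi-square test of baseline against posttreatment counts in the same women ignores the pairing. And because Table 2 has no ovarian row, the randomised comparison of ovarian change is not tabulated on any scale, while weight, hormones and lipids are kept as measured values and compared as changes.

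**Working it through.** **Inputs from the documents.** 30 women per arm (SAP Tables 1 and 2). Significance level 0.05 (SAP, Statistical method); sidedness is not stated, so two-sided is assumed. There is no power calculation to reproduce.

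**Assumed inputs.** The underlying ovarian measure is normal with equal SD before and after treatment, and the yes/no reading is a single cut on it. One arm falls by d SD and the other is unchanged, with d = 0.5 or 0.74. Baseline prevalence p is 50–90% (95% where stated), pre–post correlation r is 0.5–0.7, and there is no dropout.

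**Step 1: information kept by the cut.** For small shifts the fraction kept is φ(z_p)² / [p(1 − p)].

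- p = 0.5: 0.3989² / 0.25 = 0.64
- p = 0.7: 0.58
- p = 0.8: 0.2800² / 0.16 = 0.49
- p = 0.9: 0.1755² / 0.09 = 0.34
- p = 0.95: 0.22

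More than half is lost only from about 80% prevalence upwards.

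**Step 2: what a 0.5 SD fall looks like in counts.** Prevalence after treatment is Φ(z_p − d). For p = 0.9 this is Φ(1.282 − 0.5) = 0.783, so 27 of 30 becomes about 23.5 of 30. For p = 0.7 it is Φ(0.524 − 0.5) = 0.51.

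**Step 3: the measured value.** The SD of change is √[2(1 − r)], that is 1.00 at r = 0.5 and 0.775 at r = 0.7.

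- Paired t within an arm: noncentrality (d / SD of change) × √30. For d = 0.5 this is 2.74 and 3.54 on 29 df, giving power of about 75% and 93%.
- t-test on change between arms: noncentrality (d / SD of change) × √15. For d = 0.5 this is 1.94 and 2.50 on 58 df, giving about 48% and 69%.

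**Step 4: the yes/no analysis set against it, by direct calculation.**

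| d | r | p | Within: chi-square | Within: exact McNemar | Within: paired t | Between: chi-square on final status | Between: t on change |
|---|---|---|---|---|---|---|---|
| 0.5 | 0.5 | 0.5 | 29% | 31% | 75% | 33% | 48% |
| 0.5 | 0.5 | 0.9 | 20% | 14% | 75% | 24% | 48% |
| 0.5 | 0.7 | 0.5 | 27% | 38% | 93% | 33% | 69% |
| 0.5 | 0.7 | 0.9 | 18% | 15% | 93% | 24% | 69% |

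Simulation, which also covers intermediate prevalences, spreads a point or two wider. The ranges at 0.5 SD are then: within arm, chi-square 18–31% and exact McNemar 14–39% against paired t 74–93%; between arms, chi-square 23–34% against t on change 47–70%. A baseline-adjusted comparison reached 58–76% in simulation at prevalences of 70% and 90%.

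**Step 5: a larger fall, 0.74 SD.** Between arms: chi-square about 48–62% against t on change 79–95%. Within arm: exact McNemar about 40–75% against paired t 98–100%.

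**Step 6: the cut alone, without the benefit of baseline.** Part of the gap in Step 4 at r = 0.7 comes from the t-test using baseline while the chi-square does not. Comparing final values only (normal approximation):

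| d | Measured | Yes/no at p = 0.5 | 0.7 | 0.8 | 0.9 | 0.95 |
|---|---|---|---|---|---|---|
| 0.5 | 49% | 32% | 32% | 30% | 23% | 18% |
| 0.74 | 82% | 59% | 61% | 57% | 47% | 36% |

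At 0.74 SD the yes/no outcome keeps 61/82 = 74% of the power at p = 0.7 and 36/82 = 44% at p = 0.95. At 0.5 SD it keeps 32/49 = 65% at p = 0.7 and 23/49 = 47% at p = 0.9.

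**The case against.** The strongest case against is that the loss is easily overstated and the outcome is peripheral.

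- *A reader might infer that most of the power is lost in general.* The figures do not support that. On final values at 50–80% prevalence, the yes/no outcome keeps roughly 61–66% of the power at 0.5 SD and 70–74% at 0.74 SD. This stands.
- *A reader might infer that nearly all women are polycystic at entry because it is an entry feature.* Two of three criteria suffice, so it is optional, and baseline prevalence is not stated. This stands, and prevalence drives the size of the loss.
- *A reader might infer that recorded follicle counts and ovarian sizes are being thrown away.* The protocol does not say what the scan records and does not define the polycystic reading. A single cut on one normal measure is a simplification. What can be said is that no such values are analysed.
- *A reader might infer that the polycystic row is the only ovarian row.* The dominant-follicle row is a second one. Its source is not stated, though ultrasound is plausible, and it too is yes/no.
- *A reader might infer that a real ovarian improvement would usually be reported as no change.* At 0.5 SD within an arm the yes/no test does miss it more often than not. At 0.74 SD exact McNemar power is 40–75%, so this is not general. McNemar is also not the planned test; the SAP names only chi-square.
- *Ovarian morphology is not a named aim.* The protocol's abstract names glucose, lipids, sex hormones and menstrual cycle. That limits the weight of the point. However, the title refers to reproductive disorders and the SAP lists the ovarian rows under reproductive function.

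None of this removes the core: both ovarian rows are binary, Table 2 has none, and power was lost in every setting tried.

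**Conclusion.** The point holds as a cheap improvement to the analysis; it is not a flaw that undermines the trial. Ovarian morphology is analysed only through yes/no rows with a test that ignores pairing, and ovarian change is absent from the between-arm table.

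The cost is a substantial part of the power. It becomes most of the power in two situations: modest within-arm changes, and very high baseline prevalence. The prevalence needed for the second rises with the shift: on final values, about 90% for 0.5 SD and about 95% for 0.74 SD. These sizes rest on assumed shift, prevalence, correlation and normality, none of which the documents give. The direction of the result does not change across the ranges tried, but the exact loss does.

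**What to change.** At both planned scans, record follicle number and ovarian volume for each ovary. Prespecify how the two ovaries are combined, for example by their mean. Add both measures as continuous rows to SAP Tables 1 and 2, with volume on the log scale, and compare arms with a baseline-adjusted model. Label both as secondary, since they add to an already long list of tested rows. Keep the yes/no polycystic row as description. If a within-arm P value is still wanted for a yes/no row, use a paired test such as McNemar's instead of chi-square.

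The cost is a few extra numbers per scan and two more secondary comparisons. No extra scan or visit is needed.
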